## 9.5.2. Change from Baseline in MTD at DBPCFC

Frequencies and percent of subjects will be presented for each MTD level at the Screening and Exit DBPCFC and for all possible ratios (X-fold increase) of the MTD at the Exit DBPCFC relative to the Screening DBPCFC. In order to calculate fold, if subjects do not tolerate any dose level they will be assigned an MTD of 0.3 mg.

Analyses of change from baseline MTD will be performed using change calculated on the log10 scale. Summary statistics of the change in MTD in the log10 dose scale will be presented. As above, if subjects do not tolerate any dose level they will be assigned an MTD of 0.3 mg prior to converting to the log10 scale. An analysis of covariance (ANCOVA) model of change from screening MTD at Exit DBPCFC (log10 mg) will be fit with terms for treatment group, region, and MTD at screening (log10 mg). The values for MTD for subjects who do not undergo the Exit DBPCFC will be imputed using the MTD from their Screening DBPCFC.

The comparison of treatment groups using the ANCOVA model corresponds to the following hypotheses:

- H0: Mean change from baseline within active subjects = mean change from baseline within placebo subjects when controlling for baseline and region
- HA: Mean change from baseline within active subjects ≠ mean change from baseline within placebo subjects when controlling for baseline and region

The p-value is based on the F-test for treatment group effect adjusted for the MTD at screening ( $\log_{10}$  mg) and region. The ANCOVA model will also be assessed for unequal slopes by adding a term for the treatment group by baseline interaction and using an F-test

to test for unequal slopes. If there is a signal of unequal slopes at the 0.10 significance level, then the least squares means with 95% confidence interval, and p-value for the F-test of the treatment group difference will be calculated and reported at screening MTDs of 1 mg, 3 mg, 10 mg, and 30 mg. P-values and confidence intervals are based on the normality assumption.

Model residuals will be calculated and assessed for non-normality using the Shapiro-Wilk test and graphically to check the model assumptions of homoscedasticity and normality. If the model assumptions of homoscedasticity and normality are not met, then the Wilcoxon rank-sum test, adjusted for region will be used to test for a treatment group difference to examine the robustness of the ANCOVA F-test. Further exploration may be warranted if unequal slopes are noted.

Least squares mean statistics (point estimate and confidence interval) from the ANCOVA analysis of change from baseline analysis in the  $log_{10}$  scale will be transformed back to the original scale to obtain geometric least squares mean statistics of the ratio of AR101 to Placebo. Similarly, geometric least squares mean statistics of the ratio of the MTD at the Exit DBPCFC to Screening DBPCFC will be obtained and presented by treatment group.

Analyses will be performed in the ITT and Completer populations.

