The percentage of subjects with a maximum symptom severity grade of moderate or severe/worse was lower in the AR101-treated group than in the placebo-treated group at every peanut protein level during the Exit DBPCFC. For AR101 subjects, no subject experienced a severe/worse symptom during Exit DBPCFC, and moderate symptoms were not encountered until a dose of 600 mg. In contrast, at the time of the Exit DBPCFC, at least 1 placebo subject experienced moderate or severe/worse symptoms at each evaluated dose.

For the key secondary endpoint of change from baseline in maximum tolerated dose of peanut protein at Exit DBPCFC analyzed in an analysis of covariance (ANCOVA) model, a treatment

difference of 0.912 \log_{10} mg (p < 0.0001) was observed with a change from baseline in tolerated dose of 1.254 \log_{10} mg for AR101 and 0.341 \log_{10} mg for placebo. In terms of the ratio of maximum tolerated dose (MTD) of peanut protein at the Exit DBPCFC compared to Baseline, AR101 subjects were able to tolerate 17.94 times as much peanut protein at the Exit DBPCFC compared to Baseline, while placebo subjects were able to tolerate 2.19 times as much peanut protein at the Exit DBPCFC compared to Baseline.

For the secondary endpoints of changes in peanut-specific IgE and peanut-specific IgG4 levels and related measures, the relative treatment effect was calculated as a ratio of two ratios (study exit result : baseline result in the AR101 group / study exit result : baseline result in the Placebo group) The largest relative treatment effect, 4.756, was noted for peanut-specific IgG4, reflecting study exit values that were 5-times baseline in the AR101 group compared to levels that were nearly unchanged in the Placebo group. The 95% CI around this relative treatment effect (3.271, 6.915) excluded the null value of 1.

For the secondary endpoint of changes in skin prick test (SPT) results, the difference between treatments was calculated as the change from baseline to study exit in the AR101 group minus the change from baseline to study exit in the Placebo group. At exit visit, a notable difference in the change from baseline in maximum peanut SPT wheal diameter was observed between treatment groups, with a treatment difference of -5.2 mm. The 95% CI for this treatment difference (-9.2, -1.1) excluded the null value of 0.

Safety Results:

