6.6.2 Exit Double-Blind, Placebo Controlled Food Challenge (DBPCFC)

The Exit DBPCFC will be conducted in a manner similar to the Screening DBPCFC, but starting at a dose of 3 mg of peanut protein (except for subjects who failed their Screening DBPCFC at 1 mg), and with the last 3 challenge doses progressing from 300 mg (443 mg cumulative) to 600 mg (1043 mg cumulative) and then to 1000 mg (2043 mg cumulative) of peanut protein as shown in **Table 6-1**.

The same vehicle food should be used for the Exit DBPCFC as was used for the Screening DBPCFC.

Dosing with study product should continue on the days between the two parts of the Exit DBPCFC, according to the same dosing guidelines that apply throughout the Maintenance Period.

Subjects who failed their Screening DBPCFC at the 1 mg challenge dose of peanut protein will be required to start the Exit DBPCFC with a 1 mg dose. At the investigator's discretion, a 1 mg dose may be added at the beginning of the escalation (for a maximum cumulative dose of 2044 mg peanut protein) of any subject's Exit DBPCFC.

Subjects will be considered desensitization responders for the primary endpoint analysis for North America or Europe if they are able to tolerate an Exit DBPCFC challenge dose of 600 mg (1043 mg cumulative) or 1000 mg (2043 cumulative) of peanut protein with no, or only mild, symptoms, respectively.

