#### 7.3. MAXIMUM TOLERATED DOSE AT DBPCFC

The MTD for a DBPCFC is defined as the maximum single dose of peanut protein resulting in no more than mild symptoms and assessed by the investigator to have been tolerated (i.e., subject did not experience any dose-limiting symptoms). Any symptom requiring treatment is inherently dose-limiting; thus, a dose during a DBPCFC cannot be considered "tolerated" if treatment was deemed necessary by the investigator. The MTD at the Screening DBPCFC will be used as the baseline amount of peanut protein tolerated. If a subject is administered non-standard doses at a DBPCFC, the MTD will be considered as the highest standard dose (whether administered or not) less than the highest tolerated nonstandard dose.

When describing the MTD at the Exit DBPCFC, in terms of the cumulative amount of peanut protein, the 1 mg dose will not be included. Thus subjects who tolerate all dose levels from 3 mg to 300 mg or 1 mg to 300 mg have a cumulative MTD of 443 mg.

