#### 9.5.1. Maximum Tolerated Dose at Screening and Exit DBPCFCs

The Screening and Exit DBPCFCs are based on a modified PRACTALL dosing regimen as described in section 2.7 (see Table 2.4). With the exception of the 600 mg dose, the modified PRACTALL doses are approximately on a logarithmic scale.

Estimates for the probability of tolerating each challenge dose or higher in the Exit DBPCFC will be based on the discrete hazards model with terms for treatment group effect, region (NA, EU), and the MTD at the Screening DBPCFC (baseline) in the log10 scale (Chinchilli et al., 2005). Following Chinchilli, the extreme value hazard function will be used for the discrete-time hazard function and the model will be fit with logistic regression with the complementary log-log link function. Subjects with no dose eliciting response at the 1000 mg single dose will be censored at that dose.

The probability estimates for each dose level will be tabulated by treatment group based on LS Mean estimates from the above model (i.e., adjusted for the MTD at baseline and region). The adjusted probability estimates will also be plotted. An unadjusted probability estimate will also be calculated by removing the MTD at baseline and region terms from the model. All subjects in the analysis population are considered eligible for the 1 mg dose. If the optional 1 mg dose was not taken, the subject is considered to have passed it.

The treatment group effect will be assessed using the model with terms to adjust for the MTD at baseline and region. The hazard ratio for the treatment group effect with its 95% confidence interval and the p-value will be based on the Wald statistic. If a subject did not participate in the Exit DBPCFC, the screening results will be used.

The hazard ratio is an estimate of the ratio of the conditional probability of not tolerating a single dose of the DBPCFC given the subject tolerated the lower doses for AR101 subjects relative to Placebo subjects. The comparison of treatment groups using the discrete hazards model corresponds to the following hypothesis:

- $H_0$ : The hazard ratio for subjects within active subjects relative to placebo subjects = 1 when controlling for baseline MTD and region
- $H_A$ : The hazard ratio for subjects within active subjects relative to placebo subjects  $\neq$  when controlling for baseline MTD and region

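### Read literally, SAP 9.5.2 scores an untaken 1 mg Exit dose plus failure at 3 mg as an MTD of 0.3 mg, while SAP 9.5.1 counts 1 mg as passed; the MTD change may be modestly overstated in AR101's favour

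*SAP*

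**What the plan says.** Protocol 6.6.2 has the Exit challenge begin at 3 mg by default. Subjects who failed 1 mg at Screening "will be required to start the Exit DBPCFC with a 1 mg dose". For anyone else the dose is optional: "At the investigator's discretion, a 1 mg dose may be added at the beginning of the escalation". A subject who starts at 3 mg is therefore one who did not fail 1 mg at Screening and for whom the investigator did not add it.

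Three SAP sections bear on how that subject is scored after failing 3 mg.

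- SAP 7.3 defines the MTD as the "maximum single dose of peanut protein resulting in no more than mild symptoms and assessed by the investigator to have been tolerated". It has no rule for a skipped 1 mg dose. Its allowance for doses not actually given concerns non-standard dosing only.
- SAP 9.5.1 (discrete hazards model): "If the optional 1 mg dose was not taken, the subject is considered to have passed it".
- SAP 9.5.2 (fold table and ANCOVA): "if subjects do not tolerate any dose level they will be assigned an MTD of 0.3 mg". The same floor is applied again before the log10 conversion, and the 9.5.1 rule is not mentioned.

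Subjects with no Exit challenge are handled separately: "The values for MTD for subjects who do not undergo the Exit DBPCFC will be imputed using the MTD from their Screening DBPCFC". The ANCOVA description in Protocol 9.2.2.2 contains no floor value and does not settle the matter.

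**The concern.** The two analyses are the first two of the other secondary endpoints and are tested one after the other in the hierarchy (SAP 3.2.2 and 9.5). They should rest on the same MTD for the same challenge result. A programmer who follows 7.3 and 9.5.2 to the letter finds no tolerated dose for a subject who skipped 1 mg and failed 3 mg, and codes 0.3 mg. Under 9.5.1 that subject has passed 1 mg.

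The 0.3 mg score has two awkward results. A subject who failed at 3 mg at both Screening and Exit is recorded as having declined. And because the 1 mg dose is discretionary for most subjects, an identical failure at 3 mg can score 1 mg or 0.3 mg depending on the investigator's choice of starting dose.

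What is at stake is the ANCOVA treatment difference, its back-transformed ratio and the fold table. If these failures occur mainly on placebo, the scoring moves all three towards AR101.

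**Working it through.** **Plan's own figures.** The documents state no power or expected effect for this endpoint in ARC003. The only figures are from ARC001 (Protocol 1.2.2.1): changes of 1.254 and 0.341 log10 mg, difference 0.912, or 17.94-fold and 2.19-fold. Check: 10^1.254 = 17.95, 10^0.341 = 2.19, and 1.254 - 0.341 = 0.913. These agree to rounding.

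**Per subject.** For a subject who starts Exit at 3 mg and fails it, the scored change is log10(Exit MTD / Screening MTD):

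| Screening MTD (mg) | Exit scored 0.3 mg | Exit scored 1 mg | Gap |
|---|---|---|---|
| 1 | -0.523 | 0 | 0.523 |
| 3 | -1.000 | -0.477 | 0.523 |
| 10 | -1.523 | -1.000 | 0.523 |
| 30 | -2.000 | -1.477 | 0.523 |

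The gap is always log10(1/0.3) = 0.523. In the first row the failing dose is 3 mg on both occasions, so the whole scored fall, 70% on the mg scale, comes from the scoring rule. In the other rows the tolerated dose did fall, and only the last 0.523 is in dispute.

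**Ordering.** A subject who failed 1 mg at Screening must take 1 mg at Exit. If that dose is tolerated and 3 mg is not, the Exit MTD is 1 mg. A subject who tolerated 1 mg at Screening, skips it at Exit and fails 3 mg gets 0.3 mg. Both failed at the same Exit dose, yet the one who was more sensitive at Screening has the higher Exit MTD.

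**Which arm.** In ARC001, "at least 1 placebo subject experienced moderate or severe/worse symptoms at each evaluated dose" at the Exit challenge, while AR101 subjects had no moderate symptoms below 600 mg. Subjects without an Exit challenge carry their Screening value and are not affected.

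**Treatment difference.** Let qP and qA be the shares of the placebo and AR101 arms that start at 3 mg and fail it. The difference (AR101 minus placebo) under the 0.3 mg rule exceeds that under the 1 mg rule by about 0.523 x (qP - qA). All shares below are assumed, because the documents give no ARC003 Exit distribution.

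| qP | qA | Shift (log10) | Ratio | Share of 0.912 |
|---|---|---|---|---|
| 2% | 0 | 0.010 | x1.02 | 1.1% |
| 5% | 0 | 0.026 | x1.06 | 2.9% |
| 10% | 0 | 0.052 | x1.13 | 5.7% |
| 10% | 2% | 0.042 | x1.10 | 4.6% |
| 20% | 0 | 0.105 | x1.27 | 11.5% |

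**Cross-check.** An ANCOVA on treatment and baseline was simulated with 372 AR101 and 124 placebo subjects. Screening MTDs, treatment effect and dropout were assumed, and the SD of the log10 threshold change was set at 0.4, 0.6 and 0.8. The difference was 0.92, 0.88 and 0.84 under the 0.3 mg rule and 0.86, 0.81 and 0.76 under the 1 mg rule. These gaps match the formula. Every simulated p-value was far below 0.0001 under both rules. The affected shares that this produced (11% to 18% on placebo, 0.1% to 2% on AR101) follow from the assumed distributions and are not evidence about ARC003.

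**The case against.** The strongest reply is that the sections can be read together. The skipped-dose rule stands under a heading about MTD at both challenges, immediately before 9.5.2, and SAP 9.6.6 lists 1 mg among the Exit dose levels. If the rule carries forward, a subject who skips 1 mg has passed one level and the 0.3 mg floor never applies. Nothing in 9.5.2 excludes this. That stands as a possible intention. It is not written down, however, and 7.3, the only general definition, points the other way.

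A second reply is that 1 mg is an imputation too. Such a subject's threshold is known only to be below 3 mg. Protocol 1.1 says that sensitivity can vary from day to day by up to two orders of magnitude, so tolerating 1 mg at Screening does not show that 1 mg would be tolerated at Exit. This also stands: 1 mg is the best case and 0.3 mg the worst, and the 0.3 mg value may overstate decline rather than certainly doing so.

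Third, the consequence is limited and visible. SAP 9.5 makes no label claim on this endpoint, 9.5.2 tabulates subjects at each MTD level, and 9.5.1 lists individual values. Any 1 mg doses added at the investigator's discretion shrink the affected group. All of this is true and keeps the point small, but it does not remove the double scoring.

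A reader might infer that every affected subject is given a fall of at least 0.52 log10 that nobody observed. The documents do not support that. The figure is the smallest total fall scored; the part in dispute is 0.523, and any fall beyond it is real.

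**Conclusion.** The inconsistency holds on a literal reading of SAP 7.3, 9.5.1 and 9.5.2: one Exit result, two MTDs. The 0.3 mg value may overstate decline by up to 0.523 log10 per affected subject. Only for a Screening MTD of 1 mg is the entire scored fall a product of the rule.

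The direction, towards AR101, rests on an inference from ARC001 that failures at 3 mg will be mainly on placebo. ARC001 reports symptom severity there without counts by dose, so it supports the direction and not a size. With no AR101 subjects affected, the shift is about 0.026 log10 at an assumed 5% of placebo and 0.052 at 10%, which is small against 0.912.

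It would be a further step to conclude that the test result is in doubt or that 1 mg is the true value. Neither follows. Significance is unlikely to change, the primary and key secondary endpoints do not use this score, and the true threshold is unknown. This is a minor point about the estimate and the fold table, worth correcting because it is cheap.

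**What to change.** State one Exit MTD scoring rule in SAP 7.3 for subjects who were not given 1 mg and did not tolerate 3 mg, and use it in 9.5.1, 9.5.2 and the fold table. Following the existing 9.5.1 convention, score these subjects as 1 mg and say that this is an explicit exception to the 7.3 definition. Keep 0.3 mg for subjects who failed a 1 mg dose that was administered. Report the 9.5.2 analysis with 0.3 mg for the skipped-dose group as a sensitivity analysis, and give the number of such subjects by arm.

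The cost is a sentence or two in the SAP, one rerun of the ANCOVA and probably a slightly less favourable estimate. No data collection or challenge procedure changes. SAP 6.5 already provides for documenting a change of this kind before database lock.

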9.2.2.2 Analysis of Other Selected Secondary Endpoints

- Maximum dose achieved with no or mild symptoms at Exit DBPCFC: The probability estimates for tolerating each challenge dose or higher of the Exit DBPCFC will be calculated based on the discrete hazards model in the ITT population with terms for treatment group effect, region (North America and Europe) and the MTD at the Screening DBPCFC (baseline) in the log₁₀ scale (Chinchilli et al., 2005). The extreme value hazard function will be used for the model. The probability estimates will be tabulated by treatment group and adjusted for their Screening MTD. The values for MTD for subjects who do not undergo the Exit DBPCFC will be imputed using the maximum doses of peanut protein tolerated in their Screening DBPCFC. The treatment effect hazard ratio and its 95% confidence interval (95% CI) and p-value will be based on the Wald statistic.
- Change from baseline in maximum tolerated dose (MTD) of peanut protein at DBPCFC: Analyses of change from baseline MTD will be performed using change calculated on the log₁₀ scale. An analysis of covariance (ANCOVA) model of change from baseline MTD at Exit DBPCFC (log₁₀ mg) will be fit with terms for treatment group, region, and the MTD at baseline (log₁₀ mg). The values for MTD for subjects who do not undergo the Exit DBPCFC will be imputed using the maximum doses of peanut protein tolerated in their Screening DBPCFC. The baseline adjusted least squares means with 95% CIs by treatment group and for the treatment group difference will be tabulated. The p-value is based on the F-test for treatment group effect adjusted for the MTD at baseline (log₁₀ mg). Residuals for ANCOVA will be assessed for non-normality using the Shapiro-Wilk test. If significant at the 0.05 level, then the Wilcoxon rank sum statistic will be used to test for a treatment group difference to examine the robustness of the ANCOVA F-test.

The statistical methods used for testing the remaining secondary endpoints are described in the Statistical Analysis Plan (SAP).

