#### 2.3. BRIEF DESCRIPTION OF STUDY DESIGN

This is an international, multicenter, randomized, double-blind, placebo-controlled study of the efficacy and safety of AR101 in a characterized desensitization OIT regimen in peanutallergic individuals. The study will consist of a screening phase, that includes a Screening double-blind, placebo-controlled food challenge (DBPCFC), and a double-blind OIT Treatment Phase that includes an initial escalation period, an up-dosing period, and a maintenance period, followed by an Exit DBPCFC. The DBPCFC at screening and at exit is to be performed under double-blind conditions so that neither the subject, nor the subject's caregiver, nor any of the clinic staff (save for the unblinded preparer of the challenge foods) knows which challenge contains the peanut or the placebo. See SAP section 2.7 for a summary and protocol section 6.6 for additional details of the DBPCFC.

Peanut-allergic children and adults (ages 4-55 inclusive) will have an initial screening DBPCFC of up to 100 mg (144 mg cumulative) peanut protein or placebo. Those experiencing dose-limiting symptoms at or before the 100 mg dose of peanut protein (measured as 200 mg of peanut flour) will be eligible. Those who develop dose limiting symptoms (DLSs) in reaction to the placebo part of the screening DBPCFC will not be eligible. See Protocol Section 4 for a complete list of inclusion and exclusion criteria.

Approximately 500 peanut-allergic subjects will be randomized 3:1 to peanut OIT versus placebo. At least 80% of the subjects randomized will be children. All eligible subjects will receive escalating doses of either AR101 or placebo. The Treatment Phase comprises 3 periods:

- **Initial Escalation Period** 2 days in duration;
- Up-dosing Period This is defined as the time from the subject's first home dose of study product at 3 mg to the subject's first in-clinic dose at 300 mg, ideally 20

weeks in duration, but may be extended to a maximum of 40 weeks to accommodate dose reductions and re-escalations, if necessary;

• **Maintenance Period** – The Maintenance Period starts with the first home dose of 300 mg. Ideally, it will be 24 weeks in duration, but it may be extended by up to an additional 4 weeks (for a maximum Maintenance Period duration of 28 weeks), or to a total Treatment Phase duration of 68 weeks, whichever occurs first, to accommodate dose reductions and re-escalations that may occur during the final weeks of the Maintenance Period.

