**Europe:** Based on preliminary data from ARC002, 40 out of 55 subjects treated in ARC001 and ARC002 with AR101 underwent an Exit DBPCFC with a single dose of 1000 mg (2043 mg cumulative) of peanut protein after approximately 12 or more weeks of maintenance dosing at 300 mg/d. Of these, 24 subjects tolerated a single dose of 1000 mg (2043 mg cumulative) of peanut with no more than mild symptoms. This corresponds to an AR101 response rate of 44% (95% CI of 30% to 58%). We assume a placebo response rate of 15% at a single dose of 1000 mg (2043 mg cumulative) of peanut protein (two-thirds of what we assumed for the placebo response rate at a single dose of 600 mg [1043 mg cumulative]). A sample size of 495 children, aged 4 to 17 years, provides at least 93% power to detect an AR101 response rate of at least 30% at a single dose of 1000 mg (2043 mg cumulative) of peanut protein when the placebo response rate is at most 15%.

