# 9.5.4. Peanut-specific IgE and IgG4

Blood samples to measure ps-IgE, ps-IgG4 levels, and total IgE levels will be collected prior to the Screening DBPCFC and prior to the Exit DBPCFC. Ps-IgE/IgG4 ratio will be calculated, listed by subject, and summarized by visit and treatment group. Results outside the limits of quantification will be displayed as less than the lower limit of quantification (LLOQ), or greater than the upper limit of quantification (ULOQ), as appropriate. These values will be summarized as either the LLOQ or the ULOQ. If the ps-IgE or ps-IgG4 is outside of the limits of quantification, the ps-IgE/IgG4 ratio will be calculated using the LLOQ or ULOQ as appropriate.

Summary statistics, including geometric means and geometric standard deviations, will be presented by time point and treatment group.

Analyses of change from baseline ps-IgE, ps-IgG4, and ps-IgE/IgG4 ratio will be performed using change calculated on the log10 scale. An ANCOVA model of change from Screening DBPCFC to Exit DBPCFC will be fit with terms for treatment group, region,

and immunoglobulin value at Screening DBPCFC on the log10 scale. Similar analysis methods as described for the change from baseline in MTD at DBPCFC will be used. Geometric least squares mean statistics for the ratio of AR101 to Placebo and geometric least squares mean statistics for the ratio of the Exit DBPCFC to Screening DBPCFC by treatment group will be presented.

The comparison of treatment groups using the ANCOVA model corresponds to the following hypotheses:

- H0: Mean change from baseline within active subjects = mean change from baseline within placebo subjects when controlling for baseline and region
- $H_A$ : Mean change from baseline within active subjects  $\neq$  mean change from baseline within placebo subjects when controlling for baseline and region

Analyses will be performed in the ITT and Completer populations.

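### The Completer MTD confidence interval in SAP 9.5.2 pools one residual variance across 3:1 arms of probably very different spread, so it is likely to be too narrow (a precision correction to a supportive analysis)

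*SAP*

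**What the plan says.** SAP 9.5.2 fits an ANCOVA of log10 MTD change with terms for treatment, region and screening MTD. Its null is "Mean change from baseline within active subjects = mean change from baseline within placebo subjects when controlling for baseline and region". On inference it says "P-values and confidence intervals are based on the normality assumption". No arm-specific or robust variance is mentioned.

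Residuals are examined by Shapiro-Wilk and graphically. Then: "If the model assumptions of homoscedasticity and normality are not met, then the Wilcoxon rank-sum test, adjusted for region will be used", as a check on the robustness of the F-test. The point estimates, intervals and back-transformed ratios still come from the ANCOVA, whatever the check shows. On scope: "Analyses will be performed in the ITT and Completer populations".

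SAP 9.5.4 and 9.5.5 import the method for immunoglobulins and skin prick test: "Similar analysis methods as described for the change from baseline in MTD at DBPCFC will be used". Protocol 9.2.2.2 has a narrower trigger: "Residuals for ANCOVA will be assessed for non-normality using the Shapiro-Wilk test". It says nothing about unequal variances.

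SAP 9.5 does the hierarchical testing in the pediatric ITT population, puts the Completer analysis outside it, and rules out labeling claims from these endpoints.

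**The concern.** A pooled residual variance is weighted towards the larger arm. With three AR101 subjects for each placebo subject, it mostly reflects AR101 spread, while the uncertainty of the difference is driven mostly by the smaller placebo arm. If placebo is the more variable arm, the reported standard error is too small and the interval too narrow. If AR101 is the more variable arm, the interval is too wide.

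The plan looks for unequal variances but has no remedy for the interval when it finds them. The Wilcoxon test gives no interval, and it responds to a difference in distribution rather than specifically to a difference in means. At stake is the stated precision of the Completer MTD ratio. SAP 4.3 describes the Completer analyses as important for informing patients and families.

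**Working it through.** **Sample sizes and the plan's own figures.** The SAP states "Approximately 500 peanut-allergic subjects will be randomized 3:1 to peanut OIT versus placebo" and "A sample size of 495 children, aged 4 to 17 years, provides at least 93% power to detect an AR101 response rate". At 3:1, 495 children give 371:124. Farrington-Manning power at these sizes is 88.9% for North America (stated 89%) and 93.5% for Europe (stated at least 93%). The documents give no SD for MTD change and no coverage figure. The only benchmark is the 95% level in SAP 6.4.

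**AR101 Completer spread.** In ARC001, 23/23 tolerated 300 mg and 18/23 tolerated 600 mg (Protocol 1.2.2.1). In ARC001/ARC002, 24 of the 40 challenged tolerated 1000 mg (SAP 2.4). This gives about 22%, 18% and 60% at 300, 600 and 1000 mg:
- mean log10 = 0.22×2.477 + 0.18×2.778 + 0.60×3 = 2.845
- variance = 0.22×0.368² + 0.18×0.067² + 0.60×0.155² = 0.045, so SD = 0.21.

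**Placebo Completer spread.** In ARC001, 5/26 tolerated 300 mg and none tolerated 600 mg. At least one placebo subject had moderate or worse symptoms at each evaluated dose (Protocol 1.2.2.1). Take the ARC003 dose grid and read moderate or worse as not tolerated, which is the protocol's default. The least-spread arrangement that fits is then one subject each at 1, 3, 10 and 100 mg, 17 at 30 mg and 5 at 300 mg. Its mean is 1.576, its sum of squares is 8.43, and its SD is √(8.43/25) = 0.58. The raw SD ratio is therefore at least about 0.58/0.21 ≈ 2.7. Adjusting for baseline can lower the placebo residual SD.

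**Coverage formula.** Let k = n(AR101)/n(placebo) and r = SD(placebo)/SD(AR101). The reported variance of the difference, divided by its true variance, is

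q² = [((k + r²)/(k + 1))(1 + 1/k)] / (1/k + r²) = (k + r²)/(1 + k r²),

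and coverage = 2Φ(1.96q) − 1. At k = 3:

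| r | q² | True SE / reported SE | Coverage |
|---|---|---|---|
| 1 | 1 | 1.00 | 95.0% |
| 1.5 | 5.25/7.75 | 1.21 | 89.3% |
| 2 | 7/13 | 1.36 | 85.0% |
| 2.5 | 9.25/19.75 | 1.46 | 82.0% |
| 3 | 12/28 | 1.53 | 80.1% |

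Heavier AR101 dropout softens this. At k = 2.37, r = 2 gives 87.4% and r = 3 gives 83.8%.

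**Simulation of the SAP's ANCOVA** on the discrete challenge doses, 3000 trials per setting. Assumptions: screening MTD mean 0.84 and SD 0.53 log10, 7% placebo dropout, 20% of subjects in Europe.
- *Completers*, 0-8% of AR101 failing 300 mg, placebo residual SD 0.65-0.93 (r = 1.8-3.7): coverage 80.5-87.7%, true SE 1.26-1.50 times reported. With HC3: 94.4-95.4%.
- *Completers*, placebo residual SD 0.46: coverage 87%. Runs with 5-10% of AR101 failing 300 mg stayed within about 81-89%.
- *Unequal-slopes estimates* at screening MTDs of 1, 3, 10 and 30 mg: 83-88%.
- *ITT*, 21-38% AR101 dropout set to no change: r = 0.63-1.0, coverage 95.1-98.3%. Across all ITT settings tried the range was about 93-99%.

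**Wilcoxon at equal means**, 293:115, nominal 5%: it rejects 9.5% of the time at r = 2 and 11.3% at r = 3. The pooled t-test rejects 13.6% and 17.4%. These runs did not adjust for region.

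**Test decisions.** The simulated Completer difference is about 1.6-1.9 log10. In the least favourable setting that is 1.626/0.0891 = 18 true standard errors. In ITT the weakest setting gives 0.924/0.0955 = 9.7.

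**The case against.** The strongest objection is that the size rests on an assumed placebo SD and on a tight AR101 distribution. The 23/23 result came after two weeks of maintenance in a small trial. Protocol 1.4 says only that more than 95% passed at 443 mg cumulative. Moving 5 points from 1000 mg to 100 mg raises the AR101 SD from 0.21 to about 0.28, and a ratio of 1.5 gives 89-91% coverage. This stands: the coverage range is conditional and is not a result found in the documents. It does not remove the direction of the error, which the Phase 2 shares make very likely.

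It is also fair that the SAP checks homoscedasticity, assesses unequal slopes, tabulates every MTD level and analyzes MTD separately with a discrete hazards model. None of these corrects the ANCOVA interval. The patient-information rationale in SAP 4.3 is about the chance of desensitization, so it bears only indirectly on an MTD ratio.

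Three stronger readings are tempting, and the documents do not support them:
- *That the confirmatory test is inflated.* The hierarchical test is in ITT, where the pooled interval is near nominal or conservative. If treatment had no effect at all, the randomized arms would share one distribution and neither test would be inflated.
- *That the Wilcoxon test causes the under-coverage.* It yields no interval. The SAP uses it beside the F-test, not in its place.
- *That IgE, IgG4 and skin prick tests lose power.* No arm-specific SD is given for any of them.

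**Conclusion.** The concern holds as a precision correction to a supportive endpoint. If the placebo residual SD among Completers is about 0.4-0.9 log10, the nominal 95% Completer interval for the MTD difference and ratio covers roughly 80-89%, and its reported standard error should be about 1.25-1.5 times larger. If the SD ratio proves closer to 1.5 than to 2 or 3, the shortfall is at the mild end of that range or slightly milder. ITT intervals are about right or somewhat wide.

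Separately, the Wilcoxon check tests a distributional difference and does not repair the interval. The expected MTD effect is many standard errors from zero, so no MTD decision is expected to change and the confirmatory conclusion is unaffected.

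**What to change.** In SAP 9.5.2, keep the ANCOVA terms. Base the treatment p-value, the LS-mean intervals and the back-transformed ratio intervals on HC3 standard errors or arm-specific residual variances. Do this from the outset, in both ITT and Completer analyses, rather than after a residual check. Include the estimates at fixed screening MTDs if the unequal-slopes path is taken. Make the matching change in Protocol 9.2.2.2. Apply the same rule to SAP 9.5.4 and 9.5.5 for consistency, with no claim about power. If the Wilcoxon test is kept, label it a test of a distributional difference.

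The cost is a sentence in each place and a software option, with no new data. Completer MTD intervals become about 25-50% wider. ITT intervals stay about the same or narrow.
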